4. Did not undergo AV access placement in the past
5. Medically eligible to receive AVF or AVG placement as deemed by the treating nephrologist
6. Surgically eligible to receive either an AVF or an AVG
7. HD is the intended long-term modality of treatment for ESKD
8. Planning to remain within Wake Forest provided health care for at least 12 months

Exclusion Criteria

1. Presence of an AVF or AVG
2. Previous attempt(s) for AV vascular access placement
3. Native vasculature not suitable for placement of AV access
4. Imminent transplant planned (within 6 months)
5. Anticipated life expectancy <9 months

This study targets elderly population with advanced CKD and ESKD; therefore, the clinical scenario of when an elderly individual is not able to consent for himself or herself will not be uncommon. Because the study objectives will not be met without including these subjects, this study plans to enroll elderly subjects who are not able to consent for themselves. The foreseeable risks to these subjects in this study are low as is the negative impact. For elderly with impaired mental capacity, permission for study participation will be obtained from the subject's Legally Authorized Representative (LAR).

Sample Size

This pilot trial has the principal aim of testing the feasibility of randomizing initial AV access placement to an upper extremity AVG-first (intervention) or AVF-first (comparator) strategy in patients ≥ 65 years of age. For this goal, we plan to enroll 50 participants (25 per arm).

Interventions and Interactions

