Accessed November 16, 2018), satisfaction with the vascular access (using the short-form vascular access questionnaire [SF-VAQ])¹⁹, pain at the AV access site (using the Verbal Descriptor Scale [VDS] or the modified Abbey Pain Scale [mAPS] for people who cannot verbalise)^{20;21}, level of independence (using activities of daily living [ADL] and independent ADL [IADL] instruments)^{22;23}, and health-related quality of life (using the Kidney Disease Quality of Life instrument short form [KDQOL-SF] version 1.3. which consists of a generic core (Short Form-36 [SF-36]) and an 11-item kidney disease-specific scale).²⁴, participant's

individual study experience (study conduct, intervention outcomes, and intervention decisions) (using the Qualitative Study Interview designed by the PI and safety monitor). The assessment instruments (SF-VAQ, mAPS, ADL, IADL, KDQOL-SF) are summarized in Appendix B. The schedule of assessments is summarized in Appendix C.

Data Collection and Outcome Measure(s)

Data collection at enrollment: sociodemographic characteristics (age, sex, race, marital status, educational level, living arrangement); health behaviors (smoking and alcohol consumption [no, formerly, or yes]); ESKD etiology; date of HD commencement; and pre-dialysis care (first nephrology clinic visit and number of clinic visits prior to the first HD date); Charlson comorbidity index (CCI); medications (lipid lowering drugs, anticoagulants, antiplatelets); upper limb muscle strength assessed with grip-strength test in each arm using an isometric dynamometer; gait speed. The grip-strength test will be performed twice on each hand for each assessment and the mean of the two results will be used for statistical analyses; a cut-off point <16 kg in women and <26 kg in men will define muscle weakness. The four meter gait speed (4MGS) will be assessed on a flat, unobstructed four meter delineated course by trained research staff following a standard operating procedure.

Data regarding arterial and venous diameters on pre-operative ultrasound mapping, AV access date of placement, and location of AV anastomosis will be recorded for each participant. Results of blood work obtained on a monthly basis (per standard care) at the outpatient dialysis units. This includes measurements of dialysis adequacy, anemia management, and bone-mineral metabolism.

Vascular access outcomes.

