Patient-reported views on AV access outcomes (Appendix B). Pain at the AV access site during access cannulation will be assessed using the VDS or mAPS. Using VDS, pain will be categorized into four intensity levels: absent/no pain, mild pain, moderate pain, and severe pain/pain as bad as could be/extreme pain. Patients' satisfaction with the vascular access will be assessed with the SF-VAQ. Pain at the AV access site will be assessed as acute pain and chronic pain. Acute AV access pain (evaluated with VDS or mAPS) will be assessed as pain experienced during AV access cannulation; the average score obtained at 3 consecutive access cannulation sessions (initial assessment being done with the first cannulation) will be used for analysis. Chronic AV access pain will be assessed as part of the physical symptom domain with SF-VAQ.

TCVC-related outcomes: infectious (e.g., catheter exit site infection, tunnel infection, catheter-related bacteremia) and non-infectious (e.g., catheter malposition, mechanical dysfunction, catheter migration, venous thrombosis, pneumothorax, arterial puncture, hemothorax).

Clinical outcomes related to hospital admissions observed during the study period will be recorded and will include the main admission diagnosis and length of hospitalization.

All deaths that occur during the study period will be recorded and classified into six categories (Appendix E), and sub-classified as to whether death was access-related. The cause of death will be determined by the patient's primary nephrologist and/or primary doctor according to usual practice.

Analytical Plan

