Appendix B : Assessment Instruments

Appendix C : Schedule of Assessments

Appendix D: Vascular access outcomes

Appendix E: Protocol Violation, Expected Events, Cause of Death

Appendix A: Study Flow Diagram

Appendix B: Assessment Instruments

- 1) **Grip Strength Test:** a muscle strength test that uses a hand-held dynamometer to assess the upper arm grip-strength in each arm. Study participant will squeeze the dynameter as hard as possible two separate times for each arm.
- 2) The four meter gait speed (4MGS) will be assessed on a flat, unobstructed four meter delineated course by trained research staff following a standard operating procedure. Participants will be asked to walk at their usual pace from a standing start. Two trials will be completed. The arithmetic mean of the two trials will be used for analysis. Participants will be allowed to use their usual walking aids and ambulatory oxygen, with the cylinder carried by an assistant and these factors will be kept constant within person measurements on repeated walk tests. To express gait speed in ms-1, distance walked (i.e. 4 meters) will be divided by time expressed in seconds.
- 3) **Short Form Vascular Access Questionnaire (SF-VAQ):** a questionnaire that the study participant will complete that measures the participant's satisfaction with their vascular access. Participant will circle a number on the scale that indicates their level of agreement with each statement regarding physical symptoms, social functioning, complications and overall satisfaction.
- 4) **Verbal Descriptor Scale (VDS):** a scale the study participant will complete that measures their pain at the AV access site. The participant will rate their pain as either absent/no pain, mild pain, moderate pain, or severe pain/pain as bad as could be/extreme pain.
- 5) **modified Abbey Pain Scale (mAPS) :** a scale used for people who cannot verbalize that measures their pain at the AV access site. The study staff will score the scale by observing the participant's vocalization, facial expression, and body language.
- 6) **Activities of Daily Living (ADL) and Instrumental Activities of Daily Living (IADL):** these two scales measure the level of independence of the study participant. For the ADL scale, study staff will ask participants how well they can perform various daily activities such as bathing, grooming, dressing, eating, etc.

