Appendix C: Schedule of Assessments

Schedule of assessments						
Assessment	Enrollment	Week 1 or 2 after AV access placement	Week 3 after AVG placed or Week 4 after AVF placed	Week 5 or 6 after first AV access cannulation	Week 24 or 25 of AV access use	Week 24 or 25 after AV access placement if primary AV access failure
Grip strength	√	√	Evaluation at DAG to assess AV access development and suitability for cannulation	√	√	√
4MGS	√			√	√	√
VDS or mAPS		√		√	√	√
SF-VAQ		√		√	√	√
ADLs and IADLs	√				√	√
KDQOL-SF 1.3.	√				√	√
Qualitative Study Interview						
AV, arteriovenous; 4MGS, four meter gait speed; VDS, Verbal Descriptor Scale; mAPS, Modified Abbey Pain Scale; SF-VAQ, Short-form vascular access questionnaire; ADLs, Activities of daily living; IADLs, Instrumental ADLs; KDQOL-SF, Kidney Disease Quality of Life Short-form. The Qualitative Study Interview will be performed on a maximum number of 10 subjects who have been enrolled in study >6 months and have had AV access surgery and are still currently enrolled in study either during a study visit or before the subject's dialysis treatment at their respective dialysis center.						

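### Acute access pain is inconsistently defined: Appendix C does not schedule the three cannulation sessions it is built from, no rule relates VDS to mAPS, and the preoperative reference is not collected

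*Combined protocol and SAP*

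**What the plan says.** The section on patient-reported views of AV access outcomes states: "Acute AV access pain (evaluated with VDS or mAPS) will be assessed as pain experienced during AV access cannulation". It then says that "the average score obtained at 3 consecutive access cannulation sessions (initial assessment being done with the first cannulation) will be used for analysis".

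The two instruments are described as follows:
- **VDS.** The same section says: "Using VDS, pain will be categorized into four intensity levels: absent/no pain, mild pain, moderate pain, and severe pain", with further labels for the top level. Appendix B item 4 calls it "a scale the study participant will complete that measures their pain at the AV access site".
- **mAPS.** Interventions and Interactions assigns the "modified Abbey Pain Scale [mAPS] for people who cannot verbalise". Appendix B item 5 says: "The study staff will score the scale by observing the participant's vocalization, facial expression, and body language".

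No numeric codes are given for VDS and no range or scoring rule for mAPS. Nothing says how the two relate.

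Appendix C ticks VDS or mAPS in four columns, of which the first after cannulation is "Week 5 or 6 after first AV access cannulation". The Analytical Plan lists acute and chronic access pain among the outcomes compared between arms, takes preoperative assessments as the reference, and plans robust regression and non-parametric methods for arm comparisons.

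**The concern.** Three parts of the plan describe the same outcome and do not fit together.

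1. **Timing.** The definition needs ratings at the first cannulation and the two sessions that follow. The schedule that staff would work from does not contain them. A rating missed at first cannulation cannot be recovered later.
2. **Metric.** One outcome name covers a participant's own rating and a staff rating, with no coding, conversion or separate-analysis rule. If raw scores are pooled across participants, the arm comparison depends partly on who was rated with which instrument.
3. **Reference.** A preoperative value is named for pain, but none is scheduled.

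At stake is one of the named between-arm outcomes, and what the pilot can tell the larger trial about measuring it.

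**Working it through.** **Stated figures.** The plan gives no effect size, SD or precision for pain, so there is no pain figure to reproduce. Its one precision figure, an error margin of 0.138 for consent and surgery rates, follows from 1.96 × √(0.25/50) = 0.1386, apart from truncation. It does not bear on this point.

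**Step 1: definition against schedule.** The definition needs the first cannulation and the next two consecutive sessions. The Appendix C columns ticked for VDS or mAPS are:
- Week 1 or 2 after placement. This precedes the evaluation of cannulation feasibility at week 3 (AVG) or week 4 (AVF), so it would not ordinarily measure cannulation pain.
- Week 5 or 6 after first cannulation. This is weeks after the required sessions.
- Week 24 or 25 of use. This is months after them.
- Week 24 or 25 after placement, if the access failed primarily. This is not tied to a first cannulation.

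Of the three required sessions, Appendix C schedules none. Human Subjects Protection places the acute pain rating at the start of a dialysis session but does not say which sessions. Even if the definition is read as a three-session average repeated at later visits, the first set still begins at first cannulation and still has no column.

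**Step 2: size of the mixing problem.** The documents give neither a mAPS range nor a number of users, so this is an illustration over a range. Assumptions: VDS coded 0–3; mAPS running from 0 to M; raw scores pooled; 25 per arm; mAPS users at the same relative pain r as they would have on VDS; all k users in one arm; no true difference.

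Shift in that arm's mean = (k/25) × r × (M − 3). With r = 2/3:
- M = 3: 0 for any k.
- M = 6: k = 3 gives 0.12 × 2/3 × 3 = 0.24; k = 5 gives 0.40.
- M = 9: 0.48 and 0.80.
- M = 18: 1.20 and 2.00.

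With r = 1/3 each figure halves.

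**Step 3: how likely the one-sided split is.** With 25 per arm, the chance that all k users fall in the same arm is 2 × C(25,k)/C(50,k):
- k = 3: 2 × 2,300/19,600 = 0.235, about 23%.
- k = 5: 2 × 53,130/2,118,760 = 0.050, about 5%.

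**Step 4: the planned rank methods.** Suppose all k users' scores lie above every score in the other arm and nothing else differs. The probability of superiority is then k/25 + (1 − k/25) × 0.5:
- k = 3: 0.12 + 0.44 = 0.56.
- k = 5: 0.20 + 0.40 = 0.60.

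These are upper limits, against 0.50 for no difference. Ranking bounds the distortion, but any mAPS score above 3 would still outrank severe pain on VDS.

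**Step 5: the reference.** VDS or mAPS is not ticked at enrollment. The eligibility criteria exclude anyone with a previous AV access or an attempt at one, so no preoperative value of AV cannulation pain can exist.

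**The case against.** The strongest reply is that the outcome section is itself a collection instruction. It names the three sessions, and Appendix C only summarises the schedule. The week 1–2 tick need not conflict either, because Appendix B describes both scales as measuring pain at the access site, which could include post-operative pain. This is fair. A reader might infer that following the plan yields no acute pain data, and the documents do not support that. The loss arises only if Appendix C alone governs collection. What stands is that the table lacks the sessions that the definition requires.

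Second, the text averages over sessions. It does not say that VDS and mAPS scores are combined, and the planned methods are robust or rank-based. That is also right as far as it goes. Yet acute pain is one named outcome, with no rule for separating the instruments, and ranking does not place two metrics on one scale.

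Third, mAPS users may be very few. The eligibility text says that "the clinical scenario of when an elderly individual is not able to consent for himself or herself will not be uncommon", from which a reader might infer frequent mAPS use. But inability to consent is not inability to verbalise, and no number of mAPS users is given. The text makes some use foreseeable and no more. A reader might also infer that a chance imbalance would swamp any real difference. The documents state no plausible difference, and the mean shifts above assume a one-sided split and raw means.

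Finally, this is a feasibility pilot whose Analytical Plan already warns of high variability. That limits the weight of the point but does not reconcile the texts.

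**Conclusion.** Acute access pain is inconsistently and incompletely defined. The schedule conflict and the missing preoperative value are read directly from the documents and need no assumption: none of the three required sessions is scheduled, and no enrollment rating is scheduled.

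The mixing of instruments is a real gap of unknown size. On the mean scale it runs from nil to large: 0 to 1.20 points for three users in one arm, at r = 2/3 and mAPS maxima of 3 to 18. Under a rank comparison it moves the probability of superiority to at most 0.56 for three users and 0.60 for five. All of these figures rest on an assumed number of users and a one-sided split. The mean shifts rest also on an assumed VDS coding and mAPS range.

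A reader might go further and call the outcome uninterpretable. That is too strong: the sessions are named, and VDS ratings alone can be analysed once codes are stated for the four levels. Nor is averaging the three ratings an error in itself; a median or worst category would be a preference, and the latter changes the outcome.

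Feasibility endpoints, sample size and the SF-VAQ measure of chronic pain are unaffected.

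**What to change.** - **Schedule.** Reconcile Appendix C with the outcome section by adding a column for the first three consecutive cannulation sessions. State how participants with fewer than three ratings are handled.
- **Metric.** State codes for the four ordered VDS levels and compare arms on VDS with the planned non-parametric method. Report mAPS-rated participants separately, or pool them only after a pre-specified mapping to the same ordered categories. The documents give no cut-points for such a mapping, so separate reporting is the simpler course.
- **Reference.** Drop the preoperative reference for acute cannulation pain and compare post-cannulation values between arms.

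The cost is one schedule column, a few sentences in the Analytical Plan, and slightly fewer participants in the VDS comparison. The ratings are taken at dialysis sessions that participants already attend, so no visits are added.

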We will begin by examining descriptive statistics (means, standard deviations, minima, quartiles, maxima) and plots of the data (histograms and boxplots) to become familiar with the data and check for outliers. The proportion of people meeting each of the feasibility and protocol adherence endpoints with accompanying 95% confidence intervals (CI) will be calculated using skew-corrected score tests with a continuity correction. The maximum uncorrected error margin associated with the estimation of consent and surgery rates is 0.138, obtained at $p=0.5$. This suggests that CI around these estimates will be tight enough to provide meaningful guideline in the design of the larger trial. We will describe participant characteristics and evaluate reasons for protocol violations. We will calculate rates of dropout and other events, although we expect low numbers. Robust regression and non-parametric methods will be used for comparisons between randomized arms. The associations between pre-operative muscle strength (continuous or binary variable) with AV access primary outcome will be tested using logistic regression. The participants will be followed for a minimum of 12 months following index AV access placement. Participants who undergo AV access placement >90 days after randomization or who experience primary or secondary AV access failure will be analyzed as randomized in the intention-to-treat (ITT) analysis. Missing data will be handled under the missing at random (MAR) assumptions in compliance with an ITT protocol.²⁶ We will pay close attention to variables with higher rates of missingness, relative to others or display missingness patterns that deviate from the MAR assumptions since they could inform and guide the development of the larger trial. Results from the pilot analyses are likely to have high variability, but will provide valuable insight that will be considered in the design of a larger trial.

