Recruitment will be determined as the proportion of people meeting inclusion criteria who ultimately consent to randomization. We aim to consent $\geq 70\%$ of those eligible. Protocol adherence is based on the ability to undergo a graft or fistula surgery within 90 days of randomization, which we aim to attain in $\geq 70\%$ of participants. Outcomes of quality of life stratified by the type of first AV-access strategy. Changes in grip strength, pain related to the access (acute and chronic pain), patient's satisfaction with the access, changes in the level of independence (ADLs and IADLs) and HRQoL—will be compared between the two arms, with baseline (preoperative) assessments used as reference.

Subject Recruitment Methods

Clinical records of Wake Forest Nephrology practice, including WFOPD facilities, WFBMC nephrology outpatient clinics, and WFBMC nephrology inpatient service will be reviewed for eligibility. Study participants will be older adults of age ≥ 65 years with a diagnosis of incident ESKD or have advanced CKD expected to require HD initiation within 90 days of screening who meet the following additional inclusion criteria: (1) use a TCVC for HD, (2) did not undergo surgical creation of an AV access in the past, (3) are medically eligible to undergo surgery for AV access placement, and (4) are surgically eligible to undergo surgical placement of AVF and AVG. Medical eligibility for surgical placement of AV access will be determined as part of standard of care for patients with ESKD. In clinical practice, this aspect takes in consideration patient's clinical prognosis (e.g., unlikely to recover kidney function, medically stable to undergo surgical placement of AV access, anticipated life expectancy ≥ 9 months) and goals of care (HD is the intended long-term modality of treatment). Surgical suitability for placement of AV access, AVF and AVG, will be determined as part of standard of care by the vascular surgeon. To make this determination, the vascular surgeon will use the results of the ultrasound vascular mapping of both upper extremities. Patients who meet all the eligibility criteria will be approached by the vascular access coordinator, study coordinator, and/or PI for explanation of study participation.

Human Subjects Protection

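### Does the single 0.138 margin misstate the precision of the consent rate, whose denominator is not the 50 enrolled?

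*Combined protocol and SAP*

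**What the plan says.** The Analytical Plan states "The maximum uncorrected error margin associated with the estimation of consent and surgery rates is 0.138", attained at p = 0.5, and concludes: "This suggests that CI around these estimates will be tight enough to provide meaningful guideline in the design of the larger trial". It does not print the n behind the figure.

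The same section defines the two rates. For consent: "Recruitment will be determined as the proportion of people meeting inclusion criteria who ultimately consent to randomization", with a target of at least 70%. For surgery: "Protocol adherence is based on the ability to undergo a graft or fistula surgery within 90 days of randomization", with a target of at least 70% of participants. The Sample Size section plans 50 participants, 25 per arm. Subject Recruitment Methods adds that "Patients who meet all the eligibility criteria will be approached by the vascular access coordinator" or other study staff, so eligibility is settled before anyone is asked to consent.

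For the analysis itself, the proportions get 95% intervals that "will be calculated using skew-corrected score tests with a continuity correction".

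**The concern.** The two rates have different denominators. Enrolled participants are the denominator for surgery but the numerator for consent. A single margin for both therefore looks like an error: it appears to use the number enrolled where the number eligible belongs.

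The mismatch can be put sharply. For consent, n = 50 and p = 0.5 cannot both hold in a trial that enrols 50. Fifty eligible people at 50% yield 25 participants, and 50 participants at 50% need 100 eligible people.

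Testing feasibility is the trial's principal aim, consent is one of the two rates with a numerical target, and 0.138 is the plan's only precision figure. If it were too small for consent, the claim that the intervals are tight enough to guide the larger trial would lose its support.

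**Working it through.** **Inputs.** Stated margin 0.138 at p = 0.5 and 95% confidence (Analytical Plan); planned enrolment 50 (Sample Size); both targets 70% (Analytical Plan). The number of eligible people is not in the documents and is assumed below.

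**Formula.** Uncorrected 95% margin = 1.96 × √(p(1 − p)/n).

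**Step 1: reproduce the plan's figure.** With n = 50 and p = 0.5, 1.96 × √(0.25/50) = 0.1386, which truncates to 0.138 and rounds to 0.139. Solving backwards, n = 0.25 × (1.96/0.138)² = 50.4. Other readings do not fit: 25 per arm gives 0.196, the Wilson score half-width at n = 50 gives 0.134, and adding a continuity correction of 1/(2n) gives 0.149. So n = 50 is an inference, but a safe one.

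**Step 2: surgery rate.** The denominator is the 50 randomised. The margin is 0.1386 at p = 0.5 and 1.96 × √(0.21/50) = 0.127 at p = 0.7.

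**Step 3: consent rate, assuming 50 enrol at the 70% target.** The eligible count is 50/0.7 = 71.4, so 71 or 72.

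| Eligible | Margin at p = 0.7 | Margin at p = 0.5 |
|---|---|---|
| 71 | 0.107 | 0.116 |
| 72 | 0.106 | 0.115 |

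At p = 0.7 the n = 50 basis is wider by a factor of 0.1270/0.1063 = 1.19 (0.1063 uses 71.4 eligible).

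**Step 4: consent rate if screening continues until 50 consent.** Then n = 50/p and the margin is 1.96 × p × √((1 − p)/50). It is 0.098 at p = 0.5 (100 eligible) and peaks at p = 2/3 (75 eligible): 1.96 × (2/3) × √((1/3)/50) = 0.107. It never reaches 0.138.

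**Step 5: when the bound could fail.** For a fixed eligible pool, 51 people give 0.137 at p = 0.5 and 50 give 0.1386. The printed 0.138 therefore covers consent at every p from 51 eligible upwards, which is about 36 consents at 70%. Now suppose only 30 consent:

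| Rate | n | p = 0.5 | p = 0.7 |
|---|---|---|---|
| Consent, fixed pool at 70% (30/0.7) | 43 | 0.149 | 0.137 |
| Surgery | 30 | 0.179 | 0.164 |

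If screening instead runs until 30 consent, the consent peak is 1.96 × (2/3) × √((1/3)/30) = 0.138, still at the stated figure.

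**Step 6: ordering.** Those who consent are a subset of those eligible, so the surgery denominator can never exceed the consent denominator. At p = 0.5 the surgery margin is therefore always at least as large as the consent margin.

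**The case for a change.** The best case for a change is that the sentence presents 0.138 as belonging to the estimation of both rates, whereas for consent it is not attained at any p once 50 enrol. A reader cannot learn from it how precisely consent will be estimated, or that this depends on how many eligible people are found. A bound printed without its n is also harder to check or update. The remedy would cost two sentences.

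Part of this stands. The n is missing, the third decimal is truncated, and the consent margin is not shown separately. But the sentence speaks of a maximum, and a maximum over two rates is the larger of them. By Step 6 that is the surgery margin, so the sentence makes no false claim about consent. Both denominators are defined in words in the same section; only the eligible count is absent, and it cannot be known before screening. A consent margin written in now would rest on an assumed pool of 71 or 72 people and on a choice between a fixed pool and screening until 50 consent, neither of which the documents settle.

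Dependence on reaching 50 is real, but it is not particular to consent: a shortfall widens the surgery margin more.

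**Conclusion.** The concern is right about where the figure comes from and wrong that anything needs correcting. The 0.138 is the n = 50 margin. It is the surgery rate's own maximum (0.139 when rounded) and a conservative bound for consent, whose margin is about 0.106 at the 70% target and at most 0.107 if screening runs until 50 consent. These consent figures assume that 50 enrol and that the eligible count follows from the consent rate.

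The direction is favourable: consent is estimated more precisely than stated, so the conclusion that the intervals are tight enough is, if anything, understated. The reported intervals will be computed from the observed counts by the score-based method already specified, and an analyst following the plan's definitions will put eligible people under consent and participants under surgery. Printing n = 50 and rounding to 0.139 would be a courtesy to the reader; it would alter no target, sample size, method, result or conclusion.

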The benefits of AVF over AVG are least certain in older adults, as age-related biological changes independently modulate patient outcomes.¹⁰ Nationally representative cohort studies of older adults with incident ESKD have shown similar patient survival between those whose first AV access placed or used was a fistula or a graft.^{11,12} Compared with grafts, fistulas fail more often and necessitate longer times and more subsequent procedures to aid development, exposing older patients to time-consuming procedures that may negatively affect upper extremity strength and erode their quality of life.¹³⁻¹⁶ Hitherto, the contribution of pre-operative muscle strength to AV access outcomes and the impact of AV access placement on upper extremity strength and self-sufficiency have not been evaluated. We propose a randomized pilot trial in older adults with pre-dialysis advanced chronic kidney disease (CKD) or incident ESKD using a TCVC for HD who had no prior AV access surgery and have upper extremity vasculature suitable for either fistula or graft placement. Participants will be randomized to receive an upper extremity AVF-first or AVG-first access for HD.

Objectives

The primary objective of this study is to prospectively evaluate patient and vascular access outcomes in a randomized intervention and in a patient population in whom fistula-first guidelines have been applied despite the lack of proven benefit and at the detriment of more access failures and procedures. Our hypothesis is that there is a bidirectional relationship between the type of first AV access and patient outcomes as follows: a) the graft-first strategy will confer a more effective transition from TCVC-based to AV access-based HD and will limit upper extremity functional impairment from protracted access development and subsequent access procedures, and b) preoperative muscle strength will impact AVF development.

Methods and Measures

Design

This randomized pilot trial will be parallel-arm in design (Appendix A). We plan to enroll 50 patients of age ≥ 65 years, with incident ESKD or advanced CKD expected to require HD initiation within 90 days of screening. Screening for potential participants will be performed

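### Does the muscle-strength regression miss hypothesis (b) because it does not name the fistula arm?

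*Combined protocol and SAP*

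**What the plan says.** The Objectives give two hypotheses. The second is confined to fistulas: "preoperative muscle strength will impact AVF development". The Background puts the question more broadly, naming as unstudied "the contribution of pre-operative muscle strength to AV access outcomes".

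The Analytical Plan has one sentence in which pre-operative strength is the predictor: "The associations between pre-operative muscle strength (continuous or binary variable) with AV access primary outcome will be tested using logistic regression". It does not restrict the fit to one arm, adjust for arm, or include a strength-by-arm term. Appendix D defines its outcomes for fistula and graft alike and labels none of them primary.

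Elsewhere the same section does mention arm: "Robust regression and non-parametric methods will be used for comparisons between randomized arms", and "Outcomes of quality of life stratified by the type of first AV-access strategy". It also compares change in grip strength between arms, but there strength is the outcome, which serves hypothesis (a).

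On measurement, Data Collection and Outcome Measure(s) says the "grip-strength test will be performed twice on each hand for each assessment", with the two results averaged, and for the binary form "a cut-off point <16 kg in women and <26 kg in men will define muscle weakness". Sample Size states the purpose of the trial: "This pilot trial has the principal aim of testing the feasibility of randomizing initial AV access placement".

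**The concern.** One of the two stated hypotheses is about fistulas, yet the sentence that should test it speaks of access in general. The two readings estimate different quantities. A both-arm slope equals the fistula slope only if strength acts equally in grafts; if it does nothing there, the both-arm slope is diluted. Because neighbouring sentences name arm and this one does not, a reader cannot tell which model was intended.

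Continuous grip raises a similar question. Men and women differ in strength, the binary cut-offs reflect this, and the sentence does not say whether sex enters the continuous model. The outcome and the hand are not named either. The worry is that a slope of unclear meaning would be carried into the design of the larger trial.

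**Working it through.** **The plan's own precision figure.** The only one is the maximum error margin of 0.138 for consent and surgery rates. With 50 participants (Sample Size) and p = 0.5: 1.96 × √(0.25/50) = 0.1386, which is the stated value truncated. The plan's precision statement concerns feasibility proportions; nothing in it is sized for a strength slope.

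**What any strength analysis can detect.** Assume two-sided α of 0.05, 80% power and an event rate of 0.3 to 0.5. For a standardised continuous predictor, the detectable log odds ratio is b = (1.960 + 0.842)/√(n p(1−p)).

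- Fistula arm, n = 25: p = 0.5 gives 2.802/√6.25 = 1.121, an odds ratio of 3.07 per SD; p = 0.3 gives 3.40.
- Both arms, n = 50: p = 0.5 gives 2.802/√12.5 = 0.792, an odds ratio of 2.21; p = 0.3 gives 2.37. This is for a different quantity.
- Strength-by-arm term, p = 0.5 in both arms: SE = √(1/6.25 + 1/6.25) = 0.566, and exp(2.802 × 0.566) = 4.88 as a ratio of odds ratios. It reaches 6.42 with event rates of 0.3 (fistula) and 0.2 (graft).

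**Which model does better.** This was simulated with 25 per arm and a penalised likelihood-ratio test. Assumptions: half women; grip 16 ± 5 kg in women and 27 ± 8 kg in men; 57.5% success per arm; fistula odds ratio 2.0 per 5 kg. Ranges cover success driven by absolute or by sex-relative strength, with and without sex in the model.

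| Strength effect in grafts | Fistula-arm power | Both-arm power |
|---|---|---|
| None | 27-64% | 16-34% |
| Same as in fistulas | 26-62% | 53-94% |

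With no graft effect the both-arm slope is 0.42-0.49 of the fistula slope. The power ordering reverses at a graft slope of about one third of the fistula slope. At one half, the both-arm model has more power but returns only 0.73-0.76 of the fistula slope.

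**How large the assumed effect is.** The grip variance is (25 + 64)/2 + (11/2)² = 44.5 + 30.25 = 74.75, so the SD is 8.65 kg. An odds ratio of 2.0 per 5 kg is then 2^(8.65/5) = 3.3 per SD, which is large. With smaller effects, no graft effect and no sex term (700 runs):

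| Odds ratio per 5 kg | Success driven by | Fistula arm | Both arms |
|---|---|---|---|
| 1.5 | absolute kg | 29% | 15% |
| 1.5 | sex-relative | 13% | 11% |
| 1.25 | absolute kg | 15% | 10% |
| 1.25 | sex-relative | 7% | 9% |

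The simulation error near 10% is about √(0.1 × 0.9/700) = 1.1 percentage points. At this end the choice of model hardly matters.

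**Sex.** At 2.0 per 5 kg with no graft effect, adding sex to the fistula-arm model cuts power from 64% to 40% if absolute strength matters, and raises it from 27% to 45% if sex-relative strength matters. The plan already allows both forms of the predictor: continuous grip gives the absolute reading, and the binary form, with its sex-specific cut-offs, gives a sex-relative one.

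**The case for a change.** The strongest case for a change is that it would cost only wording. Grip in each hand, sex and the Appendix D outcomes are already collected, and naming the fistula arm would tie the analysis to the hypothesis as written. The plan also says that the pilot's results will feed the larger trial. If strength acts only on fistulas, the dilution is real and more than halves the slope under the assumptions above.

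The textual part stands: the sentence is silent on arm, and no Appendix D outcome is labelled primary. The step from silence to defect does not. An analyst testing a hypothesis about fistula development would look at participants randomised to a fistula. Primary access failure and suitability for hemodialysis in Appendix D are the natural outcomes, and they describe largely the same event from two sides. The plan already analyses late placements and access failures as randomised. The 70% surgery target is a floor for operation within 90 days, so it gives no reason to expect only 18 of 25 fistula-arm participants in this fit.

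A fuller specification would bring problems of its own. Reporting with and without sex, and with non-operated participants both left out and counted as failures, gives 2 × 2 = 4 continuous estimates from 25 people. Unless one is named as the main estimate, the reader is no better placed to say what was planned.

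**Conclusion.** The concern does not call for a change. The plan leaves detail open in a secondary, exploratory analysis of a feasibility pilot, and whoever tests hypothesis (b) can fill it sensibly. Fistula-arm against both-arm, and sex in or out, are trade-offs whose better side depends on facts that nobody has beforehand.

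Whichever model is used, the result is an imprecise estimate. Under the 2.0-per-5-kg assumption the fistula-arm slope without sex has a median standard error of 0.283 to 0.338, so the 95% interval divides and multiplies the odds ratio by exp(1.96 × SE), or 1.74 to 1.94. An estimate of 2.0 would have an interval of about 1.0 to 3.9 at the wider end.

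The mismatch in wording rests on the text alone. Every power and slope figure rests on assumed effect sizes, success rates and grip distributions that the documents do not give, and serves only to show that neither reading dominates.
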